21. CONFLICT OF INTEREST

Alcon Japan Ltd. is sponsor of this clinical study. Alcon Japan Ltd. and head of the medical institution will sign a contract for the clinical study. Financial cost of the study will be sponsored by Alcon Japan Ltd in accordance with the contract.

Financial information to medical institutions paid by Alcon Japan Ltd. is disclosed at Homepage of Alcon Japan Ltd..

Short Title:**Statistical Analysis Plan****CLJ369-P001****Full Title:****Statistical Analysis Plan****CLJ369-P001 /****NCT03341923****Protocol Title:**

Clinical evaluation of DAILIES TOTAL1® Multifocal compared to 1-Day Acuvue® Moist® Multifocal in a Japanese population.

Project Number:

A03218

Protocol TDOC Number:

TDOC-0054350

Author:
, Japan**Template Version:**

Version 4.0, approved 16MAR2015

Approvals:

See last page for electronic approvals.

Job Notes:

This is the original (Version 1.0) Statistical Analysis Plan for this study. This version of the Statistical Analysis Plan is based on Version 1.0 of the study protocol.

Executive Summary:**Key Objectives:**

The objective of this study is to demonstrate non-inferiority of DAILIES TOTAL1® Multifocal (DT1MF) to 1-DAY ACUVUE® Moist® Multifocal (AMMF) for Investigator-graded successful lens centration in Japanese population.

Decision Criteria for Study Success:**Primary Efficacy**

Non-inferiority of DT1MF to AMMF will be demonstrated for Investigator-graded lens centration of “Optimal” after 14 days of wear with a non-inferiority margin of 10%.

[figure not shown]

Table of Contents

Statistical Analysis Plan CLJ369-P001.....	1
Table of Contents	3
List of Tables.....	4
1 Study Objectives and Design.....	5
1.1 Study Objectives.....	5
1.2 Study Description	5
1.3 Randomization.....	6
1.4 Masking	6
1.5 Interim Analysis.....	6
2 Analysis Sets.....	6
2.1 Efficacy Analysis Sets	6
2.2 Safety Analysis Set	7
2.3 Pharmacokinetic Analysis Set	7
3 Subject Characteristics and Study Conduct Summaries	7
4 Efficacy Analysis Strategy.....	7
4.1 Efficacy Endpoints	7
4.2 Efficacy Hypotheses	8
4.3 Statistical Methods for Efficacy Analyses.....	10
4.3.1 Primary Effectiveness Analysis	10
[REDACTED]	11
[REDACTED]	13
4.4 Multiplicity Strategy.....	13
4.5 Subgroup Analyses and Effect of Baseline Factors.....	13
4.6 Interim Analysis for Efficacy	13
5 Safety Analysis Strategy	13
5.1 Safety Endpoints.....	13
5.2 Safety Hypotheses	14
5.3 Statistical Methods for Safety Analyses	14
5.3.1 Biomicroscopy findings: Slit-lamp examination.....	14
5.3.2 Best corrected visual acuity with trial frames	14

5.3.3	Adverse Events.....	15
5.3.4	Device Deficiencies.....	16
5.4	Interim Analysis for Safety.....	16
6	Pharmacokinetic Analysis Strategy	16
7	Analysis Strategy for Other Endpoints	16
8	Sample Size and Power Calculations	16
9	References.....	17
10	Revision History	18

List of Tables

Table 1-1 Schedule of Study Visit.....	5

1.1 Study Objectives

The objective of this study is to demonstrate non-inferiority of DAILIES TOTAL1® Multifocal (DT1MF) to 1-DAY ACUVUE® Moist® Multifocal (AMMF) for Investigator-graded successful lens centration in Japanese population.

1.2 Study Description

This is a prospective, multi-center, single masked (subject), randomized¹ and crossover study. Subjects will be randomly assigned to one of the two orders of the investigational product wearing (DT1MF to AMMF or AMMF to DT1MF) at a ratio of 1:1 using the permuted block randomization. Subjects will wear each study article (DT1MF and AMMF) in both eyes for at least 11 days each. The randomization manager will also create the randomization code for the study eye (right or left) and maintain the key code in a masked state² until the time of code breaking.

The subject who wears habitual presbyopic soft/silicone hydrogel contact lens (multifocal lenses only) with a near spectacle ADD of +0.50D to +2.50D (inclusive) will be enrolled. The subjects will wear each of the investigational products for 14±3 days. During the observation period, the subjects remove and discard the lenses every night and use a new pair of lenses every morning. As 120 patients are required for the effectiveness assessment in this study, 134 patients will be enrolled assuming around ten percent discontinuation. One eligible eye for effectiveness analysis will be randomly selected as a study eye according to the permuted block randomization. Scheduled Visits are listed in Table 1-1, as follows.

Table 1-1 Schedule of Study Visit

Days from Dispensing		Study Visit
Visit 1	Pre-Dispensing	Visit 1: Baseline Visit
	Dispensing CL1	Visit 1: Dispensing CL1
Visit 2	14 ± 3 Days after dispensing CL1	Visit 2: Follow up CL1
	Dispensing CL2	Visit 2: Dispensing CL2
Visit 3	14 ± 3 Days after dispensing CL2	Visit 3: Follow up CL2

¹ The sequence of study lens use (DT1MF to AMMF or AMMF to DT1MF) is randomized in this study. The subjects wear the same lens in both eyes.

² The randomization code for sequence of study lens use will be masked only to the subjects. The randomization code for the target eye must be masked for the site, the subjects and sponsor.

1.3 Randomization

Subjects will be randomly assigned to one of the two orders of the investigational product wearing (DT1MF to AMMF or AMMF to DT1MF) at a ratio of 1:1 by using the permuted block randomization. Study eye (right or left) will also be randomly determined by using the permuted block randomization.

1.4 Masking

The randomization code for sequence of study lens use will be masked only to the subjects. The randomization code for the study eye must be masked to the sites, the subjects and sponsor.

1.5 Interim Analysis

No interim analyses are planned for this study.

2 Analysis Sets

Evaluability of subjects and data will be determined before breaking masked randomization codes and before locking the database lock.

2.1 Efficacy Analysis Sets

Full Analysis Set (FAS):

The Full Analysis Set (FAS) includes all randomized subjects who are exposed to any investigational product except for trial-fit lenses which is used at Visit 1 and who complete at least 1 scheduled study visit.

Per Protocol Analysis Set (PPS):

The Per Protocol Analysis Set (PPS) includes all randomized subjects who are exposed to any investigational product except for trial-fit lenses which is used at Visit 1, who complete at least 1 scheduled study visit and who do not meet any of the critical deviation or evaluability criteria identified in the Deviations and Evaluability Plan (DEP).

The FAS and the PPS will be used for primary effectiveness analysis in this study. The FAS will be used for main interpretation of primary effectiveness results. [REDACTED]

2.2 Safety Analysis Set

The pre-treatment safety analysis set will include all subjects who consented to participate in the study. The pre-treatment safety analysis set will be the set that will be used to summarize occurrence of adverse experiences prior to exposure to the investigational products. The treatment-emergent safety analysis set will include all eyes exposed to any investigational product evaluated in this study except for trial-fit lenses which is used at Visit 1.

2.3 Pharmacokinetic Analysis Set

Not Applicable.

3 Subject Characteristics and Study Conduct Summaries

For demographic factors (gender, age [40-49 years, 50-59 years, 60-69 years, \geq 70 years], type of habitual multifocal SCL/SHCL, ocular medical history, concurrent diseases, and concomitant medications), the number and percentage of subjects will be calculated for all data sets (Safety Analysis Set, FAS, and PPS). For age, diopter of habitual multifocal SCL/SHCL, average number of hours of wear per day and the average number of days of wear per week of habitual multifocal SCL/SHCL, average number of hours of wear per day and total wearing days of investigational products, corneal curvature radius (keratometry), objective refraction (refractometry), subjective refraction (spherical equivalent), best corrected visual acuity with trial frame, and diopter of dispensed lenses, descriptive statistics (arithmetic mean, standard deviation, number of subjects, median, minimum, and maximum) will be calculated.

[figure not shown]
4 Efficacy Analysis Strategy

The primary objective of this study is to demonstrate non-inferiority in investigator-graded successful lens centration of DT1MF to AMMF after 14 ± 3 days of wearing. The primary effectiveness analysis will be performed on the right or left eye that is randomly selected as a single study eye.

4.1 Efficacy Endpoints

Primary effectiveness variable is as follow.

- Investigator-graded successful lens centration of “Optimal” after 14 ± 3 days of wearing.

4.2 Efficacy Hypotheses

The primary endpoint of this study is investigator-graded successful lens centration of “Optimal” after 14 ± 3 days of wearing. The population proportion and numbers are tabulated in Table 4-1.

Table 4-1 Paired Data for Crossover Study

		AMMF		Total
		Optimal	Non-Optimal	
DT1MF	Optimal	e ($\pi 1$)	f ($\pi 2$)	$e+f$ ($\pi 1 + \pi 2$)
	Non-Optimal	g ($\pi 3$)	h ($\pi 4$)	$g+h$ ($\pi 3 + \pi 4$)
Total		$e+g$ ($\pi 1 + \pi 3$)	$f+h$ ($\pi 2 + \pi 4$)	n

$$e+f+g+h = n, \pi 1 + \pi 2 + \pi 3 + \pi 4 = 1.$$

The π . indicates the population proportion for each cell.

The null hypothesis (H0) and alternative hypothesis (H1) for the primary analysis are defined as follows:

$$\begin{aligned} H_0 \quad & \pi(DT1MF) - \pi(AMMF) \leq -10\% \\ H_1 \quad & \pi(DT1MF) - \pi(AMMF) > -10\% \end{aligned}$$

, where $\pi(DT1MF)$ and $\pi(AMMF)$ represent the population proportion of subjects rated as “Optimal” in the DT1MF and AMMF groups, respectively. $\pi(DT1MF) = \pi 1 + \pi 2$ and $\pi(AMMF) = \pi 1 + \pi 3$. Population treatment difference; $\pi(DT1MF) - \pi(AMMF) = (\pi 1 + \pi 2) - (\pi 1 + \pi 3) = \pi 2 - \pi 3$. The value of 10% is used as the non-inferiority margin.

Treatment proportion difference ($\hat{\theta}$) will be

$$\hat{\theta} = \frac{e+f}{n} - \frac{e+g}{n} = \frac{(f-g)}{n}$$

, and its asymptotic lower one-sided 97.5% confidence limit will be calculated as follows (Unmodified Wald method [Newcomb, R. G., 1998]).

$$\hat{\theta} - 1.96 \times SE$$

$$, \text{ where } SE = \{\sqrt{f+g-(f-g)^2/n}\}/n.$$

4.3 Statistical Methods for Efficacy Analyses

4.3.1 Primary Effectiveness Analysis

The primary effectiveness objective of this study is to demonstrate non-inferiority of DT1MF to AMMF for investigator-graded successful lens centration after 14 ± 3 days of wearing, more specifically, non-inferiority of DT1MF to AMMF will be demonstrated in case the lower one-sided 97.5% confidence limit of a treatment proportion difference lies above -10%.

If and only if non-inferiority is demonstrated, superiority of DT1MF over AMMF in Investigator-graded lens centration of “Optimal” will be tested. The superiority of DT1MF to AMMF will be demonstrated when a 97.5% one-sided lower confidence limit of lens difference lies above 0%.

If the Sequence (Crossover) Effect (DT1MF→AMMF vs AMMF→DT1MF) and/or the Period Effect (Visit 2 vs. Visit 3) are found to be significant, DT1MF vs AMMF will be compared at each period and/or sequence separately.

Period Effect and Sequence Effect (Crossover Effect) will be investigated with the three-way table classifying four types of response by each sequence group (Table 4-3).

Table 4-2 Analysis of Period Effect and Sequence Effect for Crossover Study

Sequence Group	Period Effect		Sub Total	Sequence Effect		Sub Total	Total
	DT1MF Optimal & AMMF Non- Optimal	DT1MF Non- Optimal & AMMF Optimal		DT1MF Optimal & AMMF Optimal	DT1MF Non- Optimal & AMMF Non-Optimal		
DT1MF→AMMF	n111	n112	n11.	n211	n212	n21.	n.1.
AMMF→DT1MF	n121	n122	n12.	n221	n222	n22.	n.2.
p-value*	0.XXXX		n1..	0.XXXX		n2..	n

[figure not shown]
*Fisher's Exact Test

If there were Period Effect and both sequence groups had propensity to have more “Optimal” in the second period, the proportion of n112 and n121 should be larger. Or, if there were Period Effect and both sequence groups had propensity to have less “Optimal” in the second period, the proportion of n111 and n122 should be larger (Mainland-Gart) [2], [3], [4].

On the other hand, if there were Sequence Effect that DT1MF had propensity to have more “Optimal” in the first period and AMMF had propensity to have more “Optimal” in the second period, the proportion of n211 and n222 should be larger. Or, if there were Sequence Effect and DT1MF had propensity to have more “Optimal” in the second period and AMMF

had propensity to have more “Optimal” in the first period, the proportion of n212 and n221 should be larger (Hills-Armitage) ^{[2], [5]}.

Fisher’s exact test will be performed to add statistical insight in addition to descriptive statistics, although the statistical power might not be necessarily maintained due to insufficient sample size.

[figure not shown]

Table 4-4 summarizes the key effectiveness analyses.

Table 4-4 Summary of Analysis Strategy for Primary [REDACTED] Efficacy Endpoints

Endpoint	Main vs. Sensitivity Approach ^a	Statistical Method ^b	Analysis Set	Missing Data Approach
Primary				
Investigator-graded successful lens centration after 14±3 days of wearing	M	Unmodified Wald method	FAS (Study Eye)	Observed data only
Investigator-graded successful lens centration after 14±3 days of wearing	S	Unmodified Wald method	PPS (Study Eye)	Observed data only
Investigator-graded successful lens centration after 14±3 days of wearing	S	Unmodified Wald method	FAS (Non-Study Eye)	Observed data only

^aM=Main analysis approach; S=Sensitivity analysis approach

^bFurther details on statistical models are:

4.4 Multiplicity Strategy

Primary analysis will be performed for a single variable, and superiority testing will be performed only when non-inferiority testing is demonstrated. [REDACTED]

[REDACTED] By defining the sequence of statistical testing in advance, the type I family-wise error (FWE) rate of [REDACTED] hypothesis tests which include primary effectiveness analyses [REDACTED] is controlled at alpha = 2.5% (one-sided). [REDACTED]

4.5 Subgroup Analyses and Effect of Baseline Factors

Subgroup analyses of the primary endpoint will be conducted to assess the consistency of treatment effect across various subgroups.

The consistency of the treatment effect of the primary endpoints will be assessed descriptively using summary statistics by category of the following subgroup factors:

- Age category (<60, 60-69, 70-79, \geq 80 years),
- Sex (Female, Male)
- Investigator

4.6 Interim Analysis for Efficacy

No interim analysis is planned.

5 Safety Analysis Strategy

5.1 Safety Endpoints

The safety endpoints are as follows.

- Biomicroscopy findings: Slit-lamp examination
- Best corrected visual acuity with trial frame
- Adverse events
- Device deficiencies

5.2 Safety Hypotheses

There are no formal safety hypotheses in this study. The focus of the safety analysis will be a comprehensive descriptive assessment of safety endpoints listed in Section 5.1.

5.3 Statistical Methods for Safety Analyses

The analysis set for all safety analyses is defined in Section 2.2. Safety variables after exposure to the test article are listed in Section 5.1. Each safety variable will be summarized descriptively.

5.3.1 Biomicroscopy findings: Slit-lamp examination

Number and percentage of presence or not presence of biomicroscopy finding will be tabulated by each investigational product and by visit. For each visit, a frequency and incidence table of the clinical diagnoses identified as biomicroscopy findings will be presented by each investigational product. Clinical diagnoses will be coded and analyzed using MedDRA.

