- [1] At unscheduled visit resulting from adverse events, etc., confirm the reason for visit and procedures taken during the visit.
- [2] Identify the type of the study lens used by the subject.
- [3] Perform examinations, assessments, or confirmations considered necessary by the investigator among those listed below:
 - Best corrected visual acuity with trial frame
 - [REDACTED]
 - Lens centration [REDACTED]
 - Slit-lamp microscopy examination (including sodium fluorescein corneal, etc.).
 - Information on the investigational products (diopter and lot number), if changed
 - [REDACTED]
- [4] Dispense the required number of the study lens to the subject, as needed.
- [5] Confirm the presence or absence of adverse events. If any adverse event is present, confirm the items in the Adverse Event CRF according to Section 10 “Adverse Events and Device Deficiencies, etc.” of the protocol.

(5) **Evaluation Method**

1) **Lens centration**

Assess lens centration for each eye by slit-lamp microscopy according to the criteria shown below.

For assessment results other than “Optimal”, check the direction of lens decentration (upward, downward, nasal, or temporal).

[figure not shown]
	Criteria
0	Centered/ Optimal
1	Slight decentration
2	Mild decentration (without limbal touch)
3	Moderate decentration (with limbal touch but without corneal exposure)
4	Severe decentration (with corneal exposure)

[figure not shown]
2) [REDACTED]

[figure not shown]
[REDACTED]

[REDACTED]

[REDACTED]

[figure not shown]
4) Fluorescein corneal and conjunctival staining

Corneal and conjunctival staining with fluorescein of both eyes will be rated by the investigator using a 5 point scale (0= Normal, 1= Trace, 2=Mild, 3=Moderate, 4=Severe).

Corneal staining with fluorescein (EFRON GRADING)

Conjunctival staining with fluorescein (EFRON GRADING)

(6) Anticipated study period

From NOVEMBER 2017 to OCTOBER 2018

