The number and percentage of subjects rated as “Optimal” in investigator-graded lens centration assessment (after 14 ± 3 day of wearing) by each investigational product will be summarized, and a difference between two investigational products will be estimated by using confidence interval based on corresponding binomial test. Non-inferiority of DT1MF to AMMF will be demonstrated in case the lower one-sided 97.5% confidence limit of a difference between investigational lenses lies above -10%. If the crossover effect (DT1MF \rightarrow AMMF vs AMMF \rightarrow DT1MF) and/or the period effect (Visit 2 vs. Visit 3) are

found to be significant, DT1MF vs AMMF will be compared at each sequence and/or period separately.

Only if non-inferiority of DT1MF to AMMF is demonstrated, superiority of DT1MF over AMMF will be tested. Superiority will be demonstrated when the lower one-sided 97.5% confidence limit for investigational lens difference lies above 0%. P-value for McNemar test is also calculated. Non-inferiority and superiority hypothetical tests in above are based on the closed testing procedure; no adjustment of significance level for each test will be made.

(4) Handling of missing data

No imputation is planned for missing data.

(5) Multiplicity

Primary analysis will be performed a single variable, and superiority testing will be performed only when non-inferiority testing is demonstrated. [REDACTED]

[REDACTED] For defining the sequence of statistical testing in advance, the type I family-wise error (FWE) rate of [REDACTED] hypothesis tests which include primary efficacy analyses [REDACTED] is controlled at $\alpha = 2.5\%$ (one-sided). [REDACTED]

(6) Safety analysis

The number and percentage of adverse events and adverse experiences which occur in the period between informed consent and before exposure to the investigational products will be presented. For the following variables, observed values and their changes from baseline will be summarized. Continuous variables will be presented descriptive statistics (arithmetic mean, standard deviation, number of subjects, median, minimum, and maximum), whereas categorical variables will be presented the number and percentage.

- Slit-lamp examination
- Best corrected visual acuity with trial frame

(7) Medical economics analysis

No medical economics analysis is planned in the study.

(8) Interim analysis

No interim analysis is planned in the study.

(9) Rationale for the sample size

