5.3.2 Best corrected visual acuity with trial frames

For best corrected decimal visual acuity with trial frame, descriptive statistics (mean, mean \pm dispersion factors (DF), N, median, min and max) will be provided.

In order to compute the mean of decimal visual acuity correctly, the geometric mean must be used for uncorrected distance visual acuity and best corrected distance visual acuity.

The formulas for transforming from decimal acuity to logMAR score and back are as follows.

$$\text{LogMAR} = -\text{Log}_{10} (\text{Decimal Acuity})$$

$$\text{Decimal Acuity} = \text{antiLog} (-\text{LogMAR}) = 10^{-\text{LogMAR}}$$

For reference, the mean of decimal acuity is defined as follows.

$$\text{Mean of Decimal Acuity} = 10^{\text{mean of} (-\text{Log MAR})} = 10^{\text{mean of Log10 (Decimal Acuity)}}$$

For geometric means, dispersion factors (DF) corresponds to standard deviations and defined as:

$$+DF = 10^{(\text{mean of Log10 (Decimal Acuity)} + \text{Log (SD)})} - 10^{\text{mean of Log10 (Decimal Acuity)}}$$

$$-DF = 10^{(\text{mean of Log10 (Decimal Acuity)})} - 10^{(\text{mean of Log10 (Decimal Acuity)} - \text{Log (SD)})}$$

where, Log (SD) is a standard deviation of Log₁₀ (Decimal Acuity).

The number and percentage of eyes with best corrected visual acuity decrease from the dispending visit to the follow-up visit will be presented by each investigational product.

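### Protocol 9(6) commits to changes from baseline for slit-lamp findings and best corrected acuity, but SAP 5.3.1 plans no within-eye change and SAP 5.3.2 no numeric acuity change

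*SAP*

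**What the plan says.** **Protocol 9(6), Safety analysis.** "For the following variables, observed values and their changes from baseline will be summarized". Two variables are listed under that sentence: slit-lamp examination and "Best corrected visual acuity with trial frame". Continuous variables get descriptive statistics, and categorical ones get counts and percentages.

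**SAP 5.3.1.** There are two outputs. The first is "Number and percentage of presence or not presence of biomicroscopy finding", split by product and visit. The second is, for each visit, "a frequency and incidence table of the clinical diagnoses identified as biomicroscopy findings will be presented by each investigational product", with MedDRA coding. No change, shift or grade is mentioned.

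**SAP 5.3.2.** There are again two outputs. The first is descriptive statistics of observed decimal acuity, using the geometric mean. The second is the number and percentage of eyes, by product, with "best corrected visual acuity decrease from the dispending visit to the follow-up visit". No threshold is given for a decrease, and no numeric change is summarised.

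**Data collected.** The notes to the examination schedule in Protocol 6(2) place fluorescein corneal and conjunctival staining within the slit-lamp examination. Under Protocol 6(5), staining in both eyes "will be rated by the investigator using a 5 point scale", running from 0 to 4.

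**The concern.** The protocol makes a specific commitment for two safety variables, and the SAP sections that should deliver it describe other outputs. SAP 5.2 says the safety endpoints will receive a comprehensive descriptive assessment, so a reader would expect to find change from baseline there.

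For slit-lamp findings, a count at each visit shows how common findings are at that visit. It does not show which eyes changed. For acuity, the count of decreases does show within-eye change, but not its size. The Lens 2 count also starts from a value taken after about two weeks of Lens 1.

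At stake is whether the safety report shows per-eye worsening by lens in the form the protocol promises. The primary centration analysis is not affected.

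**Working it through.** The plan states no figure on this point, so there is nothing to reproduce. The check compares the texts and asks what each planned table can show.

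**1. Is the mismatch explained by document versions?** The SAP is based on protocol version 1.0, and the current protocol is 1.1. The itemised changes for 1.1 concern the examination schedule table in section 6(2). They do not touch 9(6), so versioning does not explain the gap.

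**2. Side by side.**

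| Variable | Protocol 9(6) | SAP output | Left unspecified |
|---|---|---|---|
| Slit-lamp | Observed values and change from baseline | Presence/absence and coded diagnoses, by product and visit | Within-eye change; grade |
| Best corrected acuity | Observed values and change from baseline | Observed statistics; eyes with any decrease since dispensing | Numeric change; Lens 2 against Visit 1 |

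**3. What presence counts can show.** For one lens, let a be the eyes with a finding at both baseline and follow-up, b those with a new finding, and c those whose finding resolved. The tables give a + c (baseline) and a + b (follow-up). Their difference gives b − c, but b itself is not determined.

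As an assumed illustration, take 120 subjects × 2 eyes = 240 eyes, with 24 eyes showing a finding at each visit. Then b = c = 24 − a. Since a can be anything from 0 to 24, the number of eyes with a new finding can also be anything from 0 to 24. The same two table entries fit every value. Separately, an eye that moves from staining grade 1 to grade 3 reads as present at both visits, if grade 1 is counted as a finding. SAP 5.3.1 does not say whether it is.

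**4. What the acuity count can show.** Write V1, V2 and V3 for an eye's logMAR at the three visits, where higher is worse. In the visible text of Protocol 6(2) and 6(4), best corrected acuity is measured at the Visit 1 baseline and at the two follow-ups. At Visit 2 it is measured after Lens 1 is removed, and Lens 2 is dispensed at that same visit.

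- Lens 1 change since dispensing: V2 − V1. The reference is the baseline, as 9(6) requires.
- Lens 2 change since dispensing: V3 − V2. The reference is a value taken after Lens 1 wear.
- Net change: V3 − V1 = (V2 − V1) + (V3 − V2).

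If V3 − V1 is above zero, at least one of the two terms is above zero, so any net loss is counted under at least one lens. Suppose a loss L appears on Lens 1 and persists. Then V2 − V1 = L, V3 − V2 = 0 and V3 − V1 = L. The eye is counted against Lens 1, but the table shows neither the size L nor the fact that the eye is still below its Visit 1 level at Visit 3.

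**The case against.** The strongest reply has four parts.

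- **Much of 9(6) is delivered.** The SAP gives coded diagnoses and observed acuity statistics, so the observed-values half is substantially covered. This stands.
- **The acuity reference is defensible.** A period-specific reference is normal in a crossover and matches Protocol 10(3), which assigns adverse events to lenses by period. A Visit 1 reference for Lens 2 would charge a persisting Lens 1 loss to Lens 2. This also stands. A reader might infer that using Visit 2 as the reference hides acuity loss, but step 4 of the working shows that a loss on Lens 1 is counted against Lens 1.
- **Worsening has another route.** Protocol 6(4) records events that are new or aggravated after consent as adverse events, and SAP 5.3.3 tabulates eyes with ocular adverse events by product. Protocol 1(2) lists corneal epithelial staining as a possible adverse event for both lenses. This stands in part. The visible text does not say what rise in grade counts as aggravation, and the call falls to an investigator who is not masked to lens sequence.
- **Staining may be analysed elsewhere.** Protocol 1(1) names staining among the assessments to be compared with AMMF, and the SAP contents list has redacted entries between 4.3.1 and 4.4. A reader might infer that grades are analysed nowhere, and the documents do not support that.

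None of this supplies the change from baseline that 9(6) names for both variables. SAP 5.3.1 and 5.3.2 are themselves unredacted.

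**Conclusion.** The two documents conflict, and the point holds in a narrow form. SAP 5.3.1 plans no within-eye slit-lamp change, so per-eye worsening is not visible in its tables. SAP 5.3.2 plans no numeric acuity change, and its Lens 2 reference is Visit 2 rather than the protocol's baseline.

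Severity is minor. The only stated objective is non-inferiority in centration, and SAP 5.2 sets no safety hypothesis. It would go too far to conclude that worsening under a lens passes unseen, given the adverse event tables and the period-specific acuity count.

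No number of affected eyes can be given. The documents state no baseline prevalence of findings and do not say which grade counts as present. The 0-to-24 range is an assumed illustration of what the tables leave open, not an estimate. The conclusion about staining grades assumes that no redacted section already tabulates their change by eye and lens.

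**What to change.** **SAP 5.3.1.** Add, by lens, a per-eye table of change from the Visit 1 baseline to follow-up, with the number and percentage of eyes with new or worsened findings. Add a shift table of staining grade (0 to 4) unless the SAP already gives one elsewhere. Protocol 9(6) does not prescribe a shift table, but it is a direct way to show change in a graded variable.

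**SAP 5.3.2.** Keep the count of decreases since dispensing. Add a summary of logMAR change from Visit 1 to each lens's follow-up, and name the reference visit for Lens 2 in both outputs. The Lens 2 change from Visit 1 can carry over Lens 1 effects, so present it beside the period-specific change.

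If the sponsor prefers the present outputs, the SAP should state and justify the departure from Protocol 9(6).

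**Cost.** Two or three descriptive tables from data already collected at Visits 1 to 3. No new procedure and no change to sample size or error control is needed.
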